14.4 Exploratory Endpoints

Exploratory endpoints will be analyzed for the PA only, using the mITT Analysis Set.

CCI

CCI

[figure not shown]

14.5 Additional Exploratory Endpoints

CCI

CCI

14.6 LTE Efficacy Endpoints

LTE efficacy endpoints will be analyzed on mITT for the LTE Analysis only.

Same methods of imputation used for the PA will be applied to LTE analysis. However, missing efficacy assessments collected after the announcement to the sites of study early termination (i.e. 23 March 2020) will not be imputed.

Table 25 summarizes the analyses that will be performed for each LTE endpoint.

For all LTE efficacy endpoints, the baseline from the 52-weeks treatment period will be used (e.g., SRI responses, change from baseline, etc.).

Institution of EAC-determined protocol-prohibited medication/treatment (i.e., EAC-treatment failure) as well as time to first flare/flare-free/AFR will be censored at the time of announcement to the sites of study early termination (i.e., 23 March 2020).

Table 25: Analysis of LTE endpoints

Endpoint	Method
SRI response over time	
SRI response rate will be summarized over time during LTE period. The baseline from the 52-week treatment period will be used (see Section 9.6).
 
The same analysis will be repeated for subjects with a gap greater than or equal to 2 weeks between 52-week and LTE treatment periods.
 
A line plot representing the SRI response rate over time will be also provided

Low disease activity status over time	Proportions of subjects with LLDAS, SLEDAI-2K \leq 2 or clinical SLEDAI-2K \leq 2 will be summarized over time.
Change over time in CLASI-A and SLICC/ACR Damage Index Score	Descriptive statistics will be presented over time for each endpoint.
Change over time in disease activity as measured by the BILAG, SLEDAI-2K, and PGA	Descriptive statistics will be presented over time for each endpoint.
BICLA response over time	Proportion of subjects with BICLA response will be summarized over time.
Change over time in prednisone-equivalent CS dose	Descriptive statistics will be presented as detailed in Section 14.3.5. This will be applied at LTE Week 24, Week 52 and Week 104.
CCI	
Time to first flare, flare-free status and annualized flare rate	
Time to first flare, flare-free status and annualized flare rate will be analyzed as in Section 14.3.2 at Week 24, Week 52 and Week 104 with descriptive statistics only. No statistical modeling will be performed.
 
Time to first flare will be assessed starting from randomization (Day 1 of 52-week treatment period) and will be derived for the whole treatment period.
 
Flare analyses will be censored at the time of announcements to the sites of study early termination (i.e. 23 March 2020)

15 Safety Evaluation

For all safety endpoints, data selection for PA and LTE analysis will be handled as indicated in the [Table 26](#).

Table 26 : Data Handling for Safety Analysis

Data summarized	Analysis	Analysis sets	Period covered	Treatment groups

 • AEs • Laboratory data • Vital signs • ECGs • Other safety evaluations 	PA	SAF	All data from 52-week treatment period (safety follow-up included)	
 • Placebo • Evobrutinib 25 mg QD • Evobrutinib 75 mg QD • Evobrutinib 50 mg BID
	LTE analysis	LTE SAF	All data from LTE period (safety follow-up posterior to LTE included)	
 • Placebo/Evobrutinib 50 mg BID • Evobrutinib 25 mg QD/Evobrutinib 50 mg BID • Evobrutinib 75 mg QD/Evobrutinib 50 mg BID • Evobrutinib 50 mg BID/Evobrutinib 50 mg BID

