For efficacy and safety analyses, each measurement will be assigned an analysis visit number first according to the prespecified time window. The analysis visit will then be used for missing data imputations, analysis variable derivations, statistical calculations and presentations. Safety follow-up will not be included in analysis visit calculations, only assessments collected under treatment visits and no more than 14 days after last exposure date will be used.

For by visit summary of safety endpoints (e.g. laboratory and vital sign assessments), data collected during the safety follow-up will be shown, presenting separately data from subjects who completed safety follow-up and who discontinued during safety follow-up.

For subject data listings by time point, the nominal visit (as collected in the database) as well as the analysis visit will be displayed.

For the calculation of analysis visit using the time windows, 1 month is expressed as 30 days.

[figure not shown]
As the schedule of assessments is different for each visit, specific time windows must be used for each endpoint. They are defined in Appendix 18.11.

If there are multiple assessments within a same visit window, then the one closest to the target day will be used. If two assessments have the same difference with target day, the earlier one will be used.

Unblinding:

Details regarding the unblinding process are available in the Unblinding Plan.

CCI

10 Trial Subjects

The subsections in this section include specifications for reporting subject disposition and treatment/trial discontinuations. Additionally, procedures for reporting protocol deviations are provided.

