14.1.1 Definitions

The two-primary efficacy endpoints are SRI response at Week 52:

- SRI-4 response in all subjects,
- SRI-6 response in the HDA subgroup.

The SRI-4 response, a measure of reduced SLE disease activity, is defined by meeting all of the following conditions compared to Baseline:

1. ≥ 4 -point reduction in SLEDAI-2K total score.
2. No significant worsening in PGA score (< 0.3 increase assuming the PGA score is on a 0-3 scale).
3. No new BILAG A organ domain scores and ≤ 1 new BILAG B organ domain score compared to Day 1 using BILAG 2004.
4. No institution of EAC-determined protocol-prohibited medication/treatment (i.e., EAC-treatment failure)

Subjects with missing values at Week 52 after the implementation of rules defined in Appendices 18.1.1 and 18.1.3 will be considered as non-responder in the primary analysis.

Assessment of criterion #4 will be confirmed by an Endpoint Adjudication Committee (EAC). Further details can be found in the EAC Charter.

The SRI-6 response is defined similarly to SRI-4, based on a ≥ 6 -point reduction in SLEDAI-2K total score.

Details of derivation are described in Appendix 18.1.

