18.1.7 LLDAS

LLDAS status is defined as meeting all the following (Franklyn 2016):

- SLEDAI-2K ≤ 4 and no activity in any major organ systems (renal, central nervous system, cardiopulmonary, vasculitis, fever):
 - Derived from CRF form ‘SLEDAI1’, ‘SLEDAI2’, ‘SLEDAI3’ depending on the visit. In order to meet this criterion, the descriptors “seizure”, “psychosis”, “organic brain syndrome”, “visual disturbance”, “cranial nerve disorder”, “lupus headache”, “CVA”, “vasculitis”, “Urinary casts”, “hematuria”, “proteinuria”, “pyuria”, “pleurisy”, “pericarditis” & “fever” must be absent (score=0) with the exception of the following descriptors: “arthritis”, “myositis”, “rash”, “alopecia”, “mucosal ulcers”, “low complement”, “increase DNA binding”, “thrombocytopenia”, “leukopenia”. The above items can be present, however, the total score of them (if present) cannot be larger than 4, assuming all zeros being observed (i.e., absence) for the other descriptors.
- PGA ≤ 1 (scale 0-3)
- No new features of disease activity compared with the assessment of previous analysis visit
 - this criterion is derived from the SLEDAI-2K questionnaire: no new features (absent) compared with previous visit (absent = score 0 / present = score > 0) for each item
- Prednisone-equivalent ≤ 7.5 mg/day at each visit (see Table 49 and Table 50)
- No institution of EAC-determined protocol-prohibited medication/treatment (i.e., EAC-treatment failure)
 - This must be a case-by-case review and defined via Medical Review, and then confirmed by the EAC.

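### LTE response composites stop counting new treatment failures at 23 March 2020, but no matching cut-off is set for the observed disease-activity assessments that complete them

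*SAP*

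**What the plan says.** Section 14.6 contains two rules tied to the termination announcement. The first concerns the failure component and the flare endpoints: "Institution of EAC-determined protocol-prohibited medication/treatment (i.e., EAC-treatment failure) as well as time to first flare/flare-free/AFR will be censored at the time of announcement". The second concerns missing data: "missing efficacy assessments collected after the announcement to the sites of study early termination (i.e. 23 March 2020) will not be imputed".

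Table 25 in the same section then lists the LTE analyses. For SRI, "SRI response rate will be summarized over time during LTE period"; for BICLA, "Proportion of subjects with BICLA response will be summarized over time". LLDAS is treated in the same way. None of these rows carries a calendar limit. The flare row does: "Flare analyses will be censored at the time of announcements to the sites of study early termination (i.e. 23 March 2020").

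The treatment-failure component belongs to all three response definitions. SRI criterion 4 in Section 14.1.1 reads "No institution of EAC-determined protocol-prohibited medication/treatment (i.e., EAC-treatment failure"), and Appendices 18.1.7 (LLDAS) and 18.1.8 (BICLA, requirement 5) repeat it. LLDAS has a further steroid condition, "Prednisone-equivalent ≤ 7.5 mg/day at each visit".

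One general rule in Section 9.7 restricts which assessments can be assigned to an analysis visit: "only assessments collected under treatment visits and no more than 14 days after last exposure date will be used". Table 51 in Appendix 18.11 repeats this as a footnote marked on the 52-week window.

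**The concern.** A composite response keeps its meaning only if all its components are observed over the same period. Here one component has a calendar end date and the others have none. A subject who starts a prohibited medication after the announcement and is then assessed at an eligible visit can meet the SLEDAI-2K, BILAG and PGA conditions, possibly because of the new medication, and be tabulated as a responder. Had the same sequence occurred before the announcement, the subject would have been a non-responder.

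At stake is the reading of the LTE response rates over time. Visits before and after 23 March 2020 would be pooled in the same analysis windows under two different rules, with improvement on other therapy credited to evobrutinib. Section 4 says that the results go into the clinical study report and that planned analyses will also be used in submissions or manuscripts.

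**Working it through.** The plan gives no figure to reproduce, so the check is a comparison of rules followed by a calendar check that affected visits are possible.

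**Step 1: the rules side by side, for data after 23 March 2020**

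| Item | Rule in Section 14.6 |
|---|---|
| New EAC-treatment failure | Not counted |
| Flare endpoints | Whole endpoint censored |
| Missing efficacy assessment | Not imputed |
| Observed SLEDAI-2K, BILAG, PGA | No rule |

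A rule against imputing missing assessments after the announcement is needed only if visits after the announcement remain in the analysis. Table 25 puts a date limit in the flare row and none in the SRI, LLDAS or BICLA rows. The natural reading is that later observed visits are scored. This is an inference, because the SAP does not say so outright.

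**Step 2: outcome for one subject who meets every other component at the visit**

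- Prohibited medication started on or before 23 March 2020: non-responder at later visits, because that failure still counts.
- Prohibited medication started after 23 March 2020, followed by a treatment visit no more than 14 days after last exposure: responder as written.
- The same medication, but the assessment is at safety follow-up or more than 14 days after last exposure: not used (Section 9.7).
- No new prohibited medication: responder, whichever rule applies.

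Only the second case is affected. Disregarding a failure can turn a non-responder into a responder and never the reverse, so the direction is fixed. For LLDAS, the second case is blocked if the subject's prednisone-equivalent dose at the visit exceeds the stated limit.

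**Step 3: can such visits fall within the plan's own windows?**

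Inputs: last randomization date in the primary analysis cohort, 28 November 2018 (Section 6.2); announcement, 23 March 2020 (Section 4); nominal LTE Week 24 visit at LTE Day 169, with a window of LTE days 2 to 265 (Table 51). Assumption: LTE Day 1 is 364 days after randomization, with no gap.

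- LTE Day 1 for the last subject: 28 Nov 2018 + 364 days = 27 Nov 2019.
- LTE day on the announcement date: (23 Mar 2020 − 27 Nov 2019) + 1 = 117 + 1 = 118.
- Nominal LTE Week 24 visit: 27 Nov 2019 + 168 days = 13 May 2020.
- LTE entry after which the nominal Week 24 visit falls after the announcement: 23 Mar 2020 − 168 days = 7 Oct 2019, that is, randomization after 7 Oct 2019 − 364 days = 8 Oct 2018.

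For the last subject, any eligible visit from LTE Day 119 to Day 265 is after the announcement and still maps to LTE Week 24. The windows run on study day, not calendar date, so they do not remove such a visit. Affected visits are therefore possible. Their number cannot be computed, because the SAP gives neither the dates on which dosing stopped nor any count of prohibited medication started after the announcement.

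**The case against.** The strongest case on the other side has four parts.

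First, the failure criterion is frozen, not deleted. A reader might infer that later visits are scored on an SRI with one component missing. The text does not support that: failures instituted by 23 March 2020 still make the subject a non-responder, and only new ones are disregarded. This correction stands.

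Second, the route to misclassification is narrow. It needs a new prohibited medication after the announcement, then a treatment visit no more than 14 days after last exposure, and every other component met. A reader might take all subjects still in the LTE on 23 March 2020 as affected, or use the share who had not yet reached LTE Week 104 as a measure of size. Neither follows, since being in the LTE on that date implies neither an eligible later visit nor a new medication. The SAP also does not show that switching therapy was likely.

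Third, the inclusion of later observed visits is inferred from silence, and the meaning of censoring for a binary response is not defined. The EAC Charter, which is not at hand, might say more. This stands as a limit on certainty. It also counts against the plan: two programmers could follow Section 14.6 and produce different rates, one by dropping the visit and one by scoring it with failures frozen.

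Fourth, not counting therapy begun because the sponsor ended the trial is defensible, since such a switch need not mean that evobrutinib failed. That is a fair reason for censoring the failure component. By the same reasoning, disease activity measured on that therapy should not be credited as a response on evobrutinib, so it supports a common cut-off and not the present split.

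**Conclusion.** The point holds as a one-directional inconsistency in the LTE response composites. After 23 March 2020 new treatment failures are ignored while, on the natural reading, observed SLEDAI-2K, BILAG and PGA assessments still count. Any effect is toward more SRI, LLDAS and BICLA responders. It is confined to eligible visits after that date and is partly blocked for LLDAS by the prednisone limit. It also departs from the handling of flares in the same section.

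The size is unknown. The calendar check shows only that such visits fit within the plan's windows, assuming LTE entry 364 days after randomization. The consequence is limited: the LTE response analyses in Table 25 are descriptive, Section 7 describes the LTE analysis as reduced with a focus on safety, and the testing procedure in Section 14.1.2.4 covers only the two-primary and key secondary endpoints of the 52-week period. A reader might infer that the primary analysis is compromised. It is not, because the 23 March 2020 rules belong to the LTE analysis alone.

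**What to change.** Add one sentence to Section 14.6: the 23 March 2020 cut-off applies to all components of SRI, LLDAS and BICLA, so that only assessments up to and including that date enter the main LTE response summaries. Show any later visits in a separate display, labelled as scored without new treatment failures. This brings the response composites into line with the flare endpoints and removes the need to interpret censoring for a binary outcome.

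The alternative of counting every prohibited medication up to the assessment date as non-response is less attractive, because it would treat therapy started on account of the trial ending as failure of evobrutinib.

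The cost is that some post-announcement visits leave the main descriptive tables, chiefly for subjects who entered the LTE late. No new data collection is required.

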14.3.2.1 Definitions

BILAG flare severity is defined as follows:

- Severe flare: ≥ 1 BILAG A score in any organ system due to items that are new or worse, compared to the BILAG evaluation at the previous visit
- Moderate flare: at least 2 BILAG B scores in any organ systems due to items that were new or worse, and without meeting the criteria for the severe flare, compared to the BILAG evaluation at the previous visit and no BILAG A meeting the condition of severe flare
- Mild flare: 1 single BILAG B score in any organ systems due to items that were new or worse, or at least 3 BILAG C scores in any organ systems due to items that were new or worse, compared to the BILAG evaluation at the previous visit and no BILAG A and no more than one BILAG B meeting the condition of severe or moderate flare
- No flare: defined as not meeting any of the above criteria.

‘Due to items that were new or worse’ means that if the assigned Grade A/B or C contains ANY ITEM which is WORSE or NEW, such grade will be included into the flare consideration. This is valid for clinical organ domains. For laboratory organ domains (i.e. renal and hematological) where items are not worse/new, there must be an increase in score from B to A or C to B for flare to be considered.

For BILAG flares, the time to first flare is defined as follows:

Time to first flare (days) = Date of visit where the first flare has been diagnosed – Date of randomization + 1
For SFI severe flares, the time to first severe flare is defined as follows:

$$\begin{aligned} & \text{Time to first severe flare (days)} \\ &= \text{Date of first flare since last flare assessment from the SFI2 form of the eCRF} \\ & - \text{Date of randomization} + 1 \end{aligned}$$

A subject has a flare-free status at Week 52 if no flares have been reported during the 52-week treatment period. Subjects who discontinue study prior to Week 52, without having a flare are counted as not being flare-free at Week 52.

The unadjusted AFR is the total number of flares from all subjects in the analysis set, divided by the total exposure time from all subjects in the analysis set. At the subject level, the unadjusted AFR is the total number of flares experienced by the subject divided by the total exposure time of this subject.

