14.3.2.2 Statistical analysis

Table 20, Table 21 and Table 22 provide details of the Flare endpoints.

Table 20 : Time to first flare

Endpoint	Analysis method	Data Handling Notes

 Time to first severe BILAG A flare (a) Time to BILAG A or 2B Moderate to Severe flare (b) Time to first severe SFI flare (c) 	As described in Section 14.2.2.1 (no sensitivity/supportive analyses will be performed)	See Section 14.2.1 for censoring rules

(a) A Severe (BILAG A) flare is defined as at least one BILAG A score in any organ system due to items that are new or worse, compared to the BILAG evaluation at the previous visit, during the 52-week treatment period. Time to first severe BILAG A flare analysis is described in Section 14.2.2.1 as part of key secondary endpoint.
 
(b) A Moderate to Severe (BILAG A or 2B) flare is defined as at least one BILAG A grade or two BILAG B grade in any organ system due to items that are new or worse, compared to the BILAG evaluation at the previous visit.
 
(c) The severity of SFI flare is recorded in the eCRF (Mild/Moderate versus Severe). However, for statistical analysis purpose, the severity will be re-derived using the SLEDAI total score as well as each sign or symptom recorded in the SFI1, SFI2, SFI3 forms of the eCRF (see Appendix 18.1.4 for a definition of Mild/Moderate or Severe flare). As the onset of new flare date or stabilization/resolution date is not recorded in the eCRF, if an investigator records a flare in two consecutive visits, it will be assumed that the flares are distinct events (i.e., when a new SFI flare is recorded in the eCRF, it will be assumed the previous one is stabilized/resolved). Therefore, only unique records from the SFI forms of the eCRF will be counted, assuming that distinct records represent distinct flare events.
		

Table 21 : Flare free status during the 52-week Treatment Period

Endpoint	Analysis method	Data Handling Notes

 BILAG 2004 Flare-free status (a) SFI flare-free status (b) 	
 Logistic regression Descriptive statistics 	Subjects who discontinue study prior to Week 52, without having a flare are counted as not being flare-free

(a) BILAG 2004 flare-free is defined as having only BILAG scores equal to D or E during the 52-week treatment period.
 
(b) SFI flare-free is defined as having no SFI flare during the 52-week treatment period.
		

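### LTE flare-free status has two unreconciled rules for subjects stopped by the sponsor; under the imported rule or the default denominator, the percentage falls with early stopping regardless of flare control

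*SAP*

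**What the plan says.** Section 14.6, Table 25, sets the LTE method by cross-reference: "flare-free status and annualized flare rate will be analyzed as in Section 14.3.2 at Week 24, Week 52 and Week 104", with descriptive statistics only and no modelling.

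The definition in Section 14.3.2.1 reads "Subjects who discontinue study prior to Week 52, without having a flare are counted as not being flare-free at Week 52". Table 21 in Section 14.3.2.2 repeats it as the data handling note.

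Two statements in Section 14.6 then deal with the termination. The text says "time to first flare/flare-free/AFR will be censored at the time of announcement to the sites of study early termination" (23 March 2020), and Table 25 adds "Flare analyses will be censored at the time of announcements to the sites of study early termination".

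On missing data, Section 14.6 says "Same methods of imputation used for the PA will be applied to LTE analysis", but with an exception: "missing efficacy assessments collected after the announcement to the sites of study early termination (i.e. 23 March 2020) will not be imputed".

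Section 9.4 sets the default denominator. Unless otherwise stated, proportions use the number of subjects in the analysis set, and missing observations stay in the denominator as their own category. Section 8.2.2 draws the LTE analysis sets from everyone who enters the LTE.

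**The concern.** Flare-free status at LTE Week 24, 52 or 104 is a yes/no classification reported as a count and percentage. Censoring has a clear meaning for time to first flare, and the annualized flare rate can be cut at a date through its exposure time. For a binary status, censoring needs a scoring rule, and the SAP gives none. The rule it imports from 14.3.2 points elsewhere: leaving early without a flare is scored as a failure.

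The sponsor ended the study for everyone, so for most subjects stopped before a given LTE time point the reason is calendar time. If they count as failures, or stay in the denominator as missing, the LTE flare-free percentage partly measures how early a subject was randomised. Two programmers could also follow this text correctly and report different percentages from the same data.

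**Working it through.** The SAP states no LTE flare-free rate and no count of subjects reaching each LTE time point, so there is no figure to reproduce. The check has two parts.

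**1. Possible scorings.** Take a subject with no flare, still in the LTE on 23 March 2020, who has not reached the time point.

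| Reading | Basis | Effect on the percentage |
|---|---|---|
| Not flare-free | 14.3.2.1 and Table 21, via Table 25 | Pulled down |
| Missing, kept in the denominator | 14.6 (no imputation) with 9.4 | Pulled down equally |
| Removed from the denominator | One meaning of censored; not stated | Depends on how flared subjects are treated |
| Flare-free up to the censoring date | Another meaning of censored; not stated | Pushed up |

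The first two give the same percentage, because the numerator holds only subjects who reached the time point without a flare and the denominator is the analysis set. The further sentence in 9.4, that missing and non-missing totals reflect those still in the trial, does not change the percentage base.

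**2. Who could reach each time point.** Inputs:
- Announcement on 23 March 2020 (Section 14.6).
- Last randomisation in the primary analysis cohort on 28 November 2018, n = 469 (8.2.2).
- Start year 2016, because 18.8.1.2 describes 1 January 2015 as one year before the year the trial started.
- LTE visit windows from Table 51: Week 52 opens on LTE Day 266 and Week 104 on LTE Day 554.

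Assumptions: uniform accrual, no gap before the LTE, and all randomised subjects as the base, since the number entering the LTE is not given.

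Latest randomisation date = 23 March 2020 - 364 days - (LTE day - 1).
Share = accrual days up to that date / all accrual days.
There are 1,063 accrual days from 1 January 2016 and 698 from 31 December 2016.

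| LTE time point | LTE day | Latest randomisation | Start 1 Jan 2016 | Start 31 Dec 2016 |
|---|---|---|---|---|
| Week 24 | 169 | 8 Oct 2018 | 1,012/1,063 = 95.2% | 647/698 = 92.7% |
| Week 52 | 365 | 26 Mar 2018 | 816/1,063 = 76.8% | 451/698 = 64.6% |
| Week 52, window opens | 266 | 3 Jul 2018 | 915/1,063 = 86.1% | 550/698 = 78.8% |
| Week 104 | 729 | 27 Mar 2017 | 452/1,063 = 42.5% | 87/698 = 12.5% |
| Week 104, window opens | 554 | 18 Sep 2017 | 627/1,063 = 59.0% | 262/698 = 37.5% |

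Table 51 prints Day 745 for Week 104, whereas 104 x 7 + 1 = 729. Day 745 would give 41.0% and 10.2%. The last cohort subject, randomised on 28 November 2018, was at LTE Day 118 on the announcement date, about 17 weeks in.

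**Effect on the percentage.** Under either of the first two readings, the flare-free percentage = share reaching the time point x flare-free proportion among them. Suppose, for illustration only, that the proportion is 70%. At Week 104 the table would then show about 9% to 30% (0.125 x 0.70 to 0.425 x 0.70) using Day 729. Using Day 554 it would show about 26% to 41% (0.375 x 0.70 to 0.590 x 0.70). A denominator limited to subjects whose time point fell by 23 March 2020 would show about 70%.

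**The case against.** The strongest reply is that Section 14.6 makes an exception for the termination. The sentence on missing assessments follows directly after the one carrying over the primary analysis imputation and qualifies it, and two further statements censor flare analyses on the same date. A specific LTE rule would normally override a general cross-reference. The 14.3.2.1 rule is also worded for leaving before Week 52, and the LTE is offered to subjects who complete the 52-week period. Read literally, the rule reaches no LTE time point; it does so only by analogy through Table 25.

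This stands to an extent. A reader might infer that the plan definitely scores stopped subjects as failures, so that most of them cannot be flare-free at LTE Week 104. The text does not support that as a certainty. The failure scoring is one reading, and with an early-2016 start and the window opening on Day 554, more than half of the cohort could have a Week 104 assessment.

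The exception still does not repair the output. The 14.3.2.1 rule is part of the endpoint definition, not an imputation of an assessment, and nothing switches it off. If the exception does apply, the stopped subjects become missing and Section 9.4 keeps them in the denominator, with the same percentage.

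Little rests on this table, and that also stands. It is descriptive, it comes from an open-label extension, and Section 7 reduces the LTE analysis to a focus on safety. Section 14.3.2.2 also reports discontinuers among subjects with no flares, so the distortion would be partly visible. However, that count does not separate sponsor termination from other discontinuation.

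**Conclusion.** The point holds as an unresolved definition with a foreseeable downward distortion. The SAP does not say how an unflared subject stopped on 23 March 2020 is scored or counted for LTE flare-free status. Both scorings that can be traced to its text pull the percentage down for a reason unrelated to flares. Time to first flare, where censoring is well defined, is not affected, and neither is the annualized flare rate.

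Under the stated assumptions the effect is small at LTE Week 24, moderate at Week 52 and large at Week 104. The shares illustrate the size and are not bounds: the accrual shape and the start within 2016 are assumed, and the true base is LTE entrants. Subjects randomised after 28 November 2018 who entered the LTE would lower the shares.

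**What to change.** In Table 25, replace the bare cross-reference for flare-free status with an explicit rule:

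- At each LTE time point, numerator and denominator include only LTE subjects whose scheduled time point fell on or before 23 March 2020, whatever their flare status. Unflared subjects still in the LTE on that date who had not reached the time point are therefore excluded. Setting the denominator by calendar date also avoids keeping flared subjects while dropping unflared ones.
- The not-flare-free rule of 14.3.2.1 and Table 21 applies in the LTE only to discontinuations before 23 March 2020.
- Remove flare-free status from the list of endpoints to be censored.

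This is SAP wording only. The small downside is fewer subjects at LTE Week 104, so the denominator should be shown.

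A Kaplan-Meier flare-free probability censored at 23 March 2020 is an optional alternative, but it needs its own derivation. LTE time to first flare runs from randomization and some subjects had a gap before the LTE, so a time origin must be chosen. The planned time-to-flare endpoints cover severe or moderate-to-severe flares, whereas flare-free status means no flare of any severity.
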